2. LIST OF ABBREVIATIONS AND DEFINITIONS OF TERMS

The following abbreviations and specialist terms are used in this study protocol.

Abbreviation	Definition
AE	adverse event
ALT	alanine transaminase
ANC	absolute neutrophil count
AST	aspartate transaminase
BIW	twice weekly
CI	confidence interval
CPI	checkpoint inhibitor
CR	complete response
CRF	case report form
CRR	complete response rate
CT	computed tomography
CTCAE	common terminology criteria for adverse events
CTLA-4	cytotoxic T-lymphocyte-associated protein 4
DCR	disease control rate
DNA	deoxyribonucleic acid
DOR	duration of response
DSMB	Data Safety Monitoring Board
ECOG	Eastern Cooperative Oncology Group
eCRF	electronic case report form
EDC	electronic data capture
EoT	end of treatment
FDA	Food and Drug Administration
hCG	human chorionic gonadotropin
5-HT	5-hydroxytryptamine
ICF	informed consent form
ICH	International Council for Harmonisation
IEC	independent ethics committee
irAE	immune-related adverse events
IRB	institutional review board
IRC	independent review committee

Abbreviation	Definition
iRECIST	immunotherapy Response Evaluation Criteria in Solid Tumors
IST	investigator-sponsored trial
IV	intravenous
LAG-3	lymphocyte antigen 3
MAPK	mitogen activated protein kinase
mITT	modified intent-to-treat
mAb	monoclonal antibody
MedDRA	medical dictionary for regulatory activities
MRI	magnetic resonance imaging
NCCN	National Comprehensive Cancer Network
ORR	objective response rate
OS	overall survival
PD	progressive disease
PD-1	programmed cell death protein 1
PD-L1	programmed death-ligand 1
PDn	pharmacodynamic
PFS	progression-free survival
PHI	protected health information
PO	per oral
PR	partial response
PT	preferred term
QW	once weekly
Q3W	every 3 weeks
Q6W	every 6 weeks
RECIST	Response Evaluation Criteria in Solid Tumors
RNA	ribonucleic acid
SAE	serious adverse event
SAP	Statistical Analysis Plan
SD	stable disease
SINE	selective inhibitor of nuclear export
SoA	schedule of assessments
SOC	system organ class

Abbreviation	Definition
TEAE	treatment-emergent adverse event
TRAЕ	treatment-related adverse events
ULN	upper limit of normal
XPO1	exportin 1 (also called CRM1)

3. PROTOCOL SUMMARY

3.1. Synopsis

Sponsor:	Investigational Product:	Study Phase:
Karyopharm Therapeutics Inc.	Selinexor	Phase 2
Title of Study: A Phase 2 Open-Label Multicenter Study to Evaluate the Safety and Efficacy of Selinexor in Combination with Pembrolizumab in Recurrent Advanced Melanoma		
Protocol Number: XPORT-MEL-033		
Study Location: Up to 20 sites in the United States		
Study Rationale: Selinexor (XPOVIO®) is a first-in-class oral selective inhibitor of nuclear export (SINE) compound, specifically inhibiting exportin-1 (XPO1). XPO1 has a key role in nuclear export of the proteins harboring a leucine-rich nuclear export sequence. Enhanced cytoplasmic accumulation of several tumor suppressor proteins has been suggested as an additional mechanism acquired by cancer cells to attain enhanced proliferative potential. XPO1 has been identified as 1 of 7 key candidate genes that may be therapeutic targets for melanoma; in addition, XPO1 mRNA is ~2-fold overexpressed in metastatic melanoma as compared with normal melanocytes and nevi. XPO1-mediated nuclear export controls the localization of multiple proliferation-associated proteins including Rb p53, p21, p27, FOXO-3A transcription factors, mitogen-activated protein kinase/extracellular signal-regulated kinase (Mek), extracellular signal-regulated kinase (Erk) and Survivin further suggesting its potential deregulation in tumors and targetability. It has been demonstrated that XPO1 inhibition while reversing cytoplasmic Erk localization and inducing persistent Erk signaling hyperactivity induces multiple cell context-dependent molecular alterations that effect G1 arrest followed by melanoma cell apoptosis (Wu, 2019; Pathria, 2012). Programmed cell death protein 1 (PD-1) is expressed on the surface of cytotoxic T cells, and its ligand programmed death ligand-1 (PD-L1) is expressed on both melanoma tumor and immune cells. The inhibition of interactions between PD-1 and PD-L1 by agents such as nivolumab and pembrolizumab (Robert, 2015) causes the reactivation of cytotoxic T cells, leading to the recognition and destruction of melanoma cells (Hodi, 2018; Robert, 2015; Jiang, 2019; Yang, 2020). Despite the impressive activity of anti-PD-1/L1 agents in melanoma, between 40%-65% of metastatic melanoma patients are shown to be resistant to checkpoint inhibitor (CPI) mono- or combination therapy (Fenton 2019). Resistance to anti-PD-1/L1 therapy may be of three types: 
- primary resistance defined by inability of immune cells to mount an antitumor response as noted by stable disease (SD) lasting for <6 months or no response to therapy.- secondary or acquired resistance defined by confirmed objective response or prolonged SD ≥6 months but develop disease progression later.- Disease progression after discontinuation of CPI in patients who are treated with either adjuvant or neoadjuvant therapy where duration of therapy is limited. The LEAP-004 study evaluated the use of pembrolizumab with the vascular endothelial growth factor receptor (VEGFR) tyrosine kinase inhibitor (TKI) lenvatinib, in patients who had progressive disease (PD) while on anti-PD-1 mAb. The objective response rate (ORR) in advanced melanoma patients with confirmed progression on CPI therapy was 21.4% (95% CI: 13.9, 30.5) with a disease control rate (DCR) of 66.0% (95% CI: 56.0, 75.1). The median progression free survival (PFS) was 4.2 months (95% CI: 3.8, 7.1) and the median overall survival (OS) was 14.0 months (95% CI: 10.8, not reached). The majority of patients (62 out of 103; 60.2%) had primary resistance to anti-PD-1 mAb in the		

metastatic setting ([Arance, 2021](#)). Despite the improvement seen in patients with this combination, patients develop rapid disease progression and require improved treatment options.

Selinexor may overcome resistance to anti-PD-1/L1 mAbs by blocking nuclear export compounds which are implicated in regulating the inhibitory T cell receptor PD-1 and its ligand, PD-L1, such nuclear factor of activated T cells (NFAT)1c, signal transducer and activator of transcription (STAT)1 and STAT3. It is hypothesized that the retention of these regulatory compounds in the nucleus leads to an upregulation of T cell checkpoint molecule expression. This allows selinexor, when combined with anti-PD-1 mAbs, to enhance the antitumor activity ([Farren, 2017](#)).

Preclinical studies have shown that (1) XPO1 inhibitors kill malignant melanoma cells while sparing normal melanocytes and other normal cells ([Pathria, 2012](#), [Yang, 2014](#), [Breit, 2014](#)) (2) oral selinexor showed single agent anti-tumor activity at clinically relevant doses in immunocompetent mice bearing B16 melanoma tumors and did not impair anti-tumoral immunity ([Tyler, 2017](#)), (3) oral selinexor in combination with anti-PD-1 or anticytotoxic T-lymphocyte-associated protein 4 (CTLA-4) mAbs showed synergistic activity in immunocompetent mice bearing aggressive syngeneic melanoma ([Farren, 2017](#)).

The preclinical results have been borne out in early clinical studies. In a Phase 1 clinical trial of single-agent oral selinexor in patients with advanced, heavily pretreated solid tumors (KCP-330-002), a total of 14 patients with melanoma received at least 1 dose of selinexor. The ORR in these heavily pretreated patients was 14.3% with 1 patient achieving a complete response (CR) and 1 patient achieving a partial response (PR) ([Abdul-Razak, 2016](#)).

Preliminary results from the ongoing investigator-sponsored trials study (NCT02419495) evaluating selinexor 60 mg twice weekly (BIW) in combination with pembrolizumab (200 mg IV [intravenous] once every 3 weeks [Q3W]) in patients with metastatic melanoma has shown promising anti-tumor activity. Amongst the 28 patients who were evaluable for efficacy, 22 patients were diagnosed with non-uveal melanoma; 9 of them naïve to prior CPI and the other 13 were refractory to CPI therapy. The ORR among patients with CPI-naïve and CPI-refractory melanoma was 67% and 31%, respectively, with 3 CRs. The longest duration of treatment for 1 CR patient who was CPI-naïve was 17 months, with the patient withdrawing from treatment due to the CR. The median PFS was 8.8 months (95% CI: 4.2, 30.7). The range was 0.13 to 54.4. The 3-month PFS rate was 0.76 (95% CI: 0.62, 0.93). The 6-month PFS rate was 0.66 (95% CI: 0.50, 0.85). The 9-month PFS rate was 0.47 (95% CI: 0.32, 0.70). The 12-month PFS rate was 0.44 (95% CI: 0.29, 0.67). The median follow-up time was 19.1 months. The median OS was 30.7 months (95% CI: 10.2, not reached). The range was 0.13 to 54.4. The 3-month OS rate was 0.93 (95% CI: 0.84, 1). The 6-month OS rate was 0.79 (95% CI: 0.66, 0.96). The 9-month OS rate was 0.72 (95% CI: 0.57, 0.91). The 12-month OS rate was 0.68 (95% CI: 0.53, 0.88). Adverse events (AEs) in the study were similar to those reported previously for selinexor and pembrolizumab with no clear overlapping toxicities. Adverse events attributed to both pembrolizumab and selinexor included hematological toxicities, fatigue, nausea, and low sodium. Hypokalemia and gastrointestinal AEs were attributed to selinexor (data on file).

An alternative dosing regimen for selinexor in combination with pembrolizumab has been explored in the study KCP-330-027: selinexor 80 mg once weekly (QW) each week plus 200 mg pembrolizumab once every 3 weeks in patients with advanced or metastatic microsatellite stable (MSS) colorectal cancer. This combination regimen was well tolerated in the first 12 patients treated in this study. Only 1 patient had a single dose interruption due to Grade 2 nausea and then resumed the treatment at the same dose level after nausea was resolved. These findings indicate that selinexor 80 mg QW with pembrolizumab 200 mg Q3W is a tolerable regimen in patients with advanced, heavily pretreated colorectal cancer (data on file).

The preclinical and preliminary clinical data of selinexor alone and in combination with pembrolizumab indicates anti-melanoma activity and tolerability that warrant further exploration. Based on the clinical activity and the patients' tolerability seen in the clinical study KCP-330-027

[figure not shown]
mentioned above, the regimen of selinexor 80 mg QW in combination with pembrolizumab will be explored in this study. In this study, we will be using the once every six weeks (Q6W) schedule of pembrolizumab due to the approved use of the 400 mg IV dosing schedule in the US. This open label Phase 2 study is aimed to evaluate the efficacy and safety of selinexor in combination with pembrolizumab in patients with unresectable locally advanced or metastatic (Stage III or IV) melanoma that demonstrated either primary resistance to anti-PD-1/L1 mAb or acquired resistance to anti-PD-1/L1 mAb.

Overall Study Design:

Approximately 40 patients with locally advanced or metastatic melanoma will be enrolled into one of the following 2 arms:

- **Primary resistance to initial checkpoint inhibitor (CPI) therapy (Arm A):** Selinexor 80 mg orally (PO) QW+ Pembrolizumab 400 mg IV Q6W
- **Acquired resistance to initial CPI therapy (Arm B):** Selinexor 80 mg PO QW + Pembrolizumab 400 mg IV Q6W

XPORT-MEL-033 Study Design

CPI: checkpoint inhibitor; Q6W: once every six weeks; QW: once weekly

Objectives and Endpoints: The primary efficacy endpoint for this signal finding study will be ORR assessed using Response Evaluation Criteria in Solid Tumors (RECIST) v1.1 response criteria. Evaluation of the radiographic data for disease progression will be based on a scan review by the Investigator.

The objectives and endpoints for both arms to evaluate the treatment with selinexor plus pembrolizumab are the same and are listed below:

Objectives	Endpoints
Primary	

• To evaluate objective response rate (ORR) per RECIST v1.1 response criteria	
• ORR defined as proportion of patients who achieved a complete response (CR) or partial response (PR).

Secondary	

• To evaluate progression-free survival (PFS) per RECIST v1.1 response criteria• To evaluate overall survival (OS)• To evaluate rates of CR• To evaluate duration of response (DOR)• To evaluate disease control rate (DCR)	
• PFS defined as time from date of first treatment to the date of first confirmed progressive disease (PD), or death due to any cause, whichever occurs first.• OS defined as time to death, from the date of first treatment.• Complete response rate (CRR), defined as proportion of patients who achieved a CR.• DOR defined as the duration of time from first occurrence of response \geqPR until the first date of PD or death due to any cause, whichever occurs first.• Defined as the percentage of patients who have achieved CR, PR, and stable disease (SD).

• To evaluate the safety and tolerability of selinexor and pembrolizumab combination regimen.	
• Safety and tolerability of study treatment will be evaluated based on adverse events (AE) reports, vital signs, clinical laboratory results, and physical examination findings, by the occurrence, nature, and severity of AEs as categorized by the Common Terminology Criteria for Adverse Events (CTCAE) v5.0.
Exploratory	CCI

Number of Patients (planned):

Approximately 40 patients with advanced metastatic melanoma with disease resistant to CPI therapy will be enrolled.

Study Population: Eligible patients must fulfill all inclusion criteria and no exclusion criteria.

Inclusion Criteria

1. Age \geq 18 years at the time of informed consent
2. Patient must have a histologically confirmed diagnosis of locally advanced unresectable stage III or metastatic stage IV melanoma not amenable to local therapy.
 - a. Patients must have confirmed PD per RECIST on or within 12 weeks of the last dose of anti-PD-1/L1 monotherapy or combination therapy (including relatlimab or other anti-LAG-3 mAb) per Society for Immunotherapy in Cancer Guidelines ([Kluger, 2020](#))
 - b. Arm A (primary resistance): patient has disease progression after receiving at least 6 weeks of prior anti-PD-1/L1 mAb with the best response as PD, or SD<6months (patients with a PR or CR who have disease progression within 6 months will be considered to have primary resistance in this study).
 - c. Arm B (secondary/acquired resistance): patient has disease progression after receiving at least 6 months of prior anti-PD-1/L1 mAb with the best response as CR, PR, or SD>6 months (patients who have disease progression after neoadjuvant or adjuvant therapy, will be considered to have secondary resistance in this study).
 - d. Patients who progress on or within 12 weeks after elective discontinuation of anti-PD-1/L1 mono or combination treatment in the absence of PD or treatment limiting toxicity must have confirmed PD per RECIST.
3. Patients should have at least 1 prior line of CPI therapy but no more than 2.
4. Measurable disease according to RECIST v1.1.
5. Patients with stable previously treated brain metastases are permitted in this study.
6. Eastern Cooperative Oncology Group (ECOG) performance status \leq 1

7. Adequate bone marrow function at screening, defined as:
 - a. Absolute neutrophil count (ANC) $\geq 1.5 \times 10^9/L$
 - b. Hemoglobin $\geq 10 \text{ gm/dL} (\geq 6.2 \text{ mmol/L})$
 - c. Platelet count $\geq 100 \times 10^9/L$
8. Serum direct bilirubin $\leq 1.5 \times \text{ULN}$; AST and ALT $\leq 2.5 \times \text{ULN}$ (with confirmed liver metastases: AST and ALT $\leq 5 \times \text{ULN}$)
9. Calculated creatinine clearance (CrCl) $\geq 15 \text{ mL/min}$ based on the Cockcroft and Gault formula.
10. Female patients of childbearing potential must have a negative serum pregnancy test at screening and agree to use highly effective methods of contraception throughout the study and for at least four months following the last dose of study treatment. Childbearing potential excludes: age >50 years and naturally amenorrhoeic for >1 year, or previous bilateral salpingo-oophorectomy, or hysterectomy.
11. Male patients who are sexually active must use highly effective methods of contraception throughout the study and for at least four months following the last dose of study treatment. Male patients must agree not to donate sperm during the study treatment period.
12. Written informed consent signed in accordance with federal, local, and institutional guidelines

Exclusion Criteria

1. Metastatic uveal or ocular melanoma.
2. Active central nervous system (CNS) metastases or other CNS (e.g., meningeal) involvement.
3. Patients must have resolution or improvement of immune-mediated treatment-related adverse reactions related to prior treatment(s) to Grade ≤ 1 without steroid maintenance therapy or his or her previous baseline prior to the corresponding CPI therapy
 - a. History of immune-mediated treatment-related adverse reactions leading to discontinuation of prior anti-PD-1, anti-PD-L1, or anti-PD-L2 mAbs or severe hypersensitivity reaction to any mAb or any excipients which in the opinion of the Investigator precludes future use of anti-PD-1/PD-L1 therapy.
4. Concurrent systemic steroid therapy higher than physiologic dose ($> 10 \text{ mg/day}$ of prednisone or equivalent).
5. Previous treatment with selinexor or other XPO1 inhibitors.
6. Insufficient time since or not recovered from procedures or anti-cancer therapy, defined as:
 - a. Not recovered from major surgery ≤ 28 days prior to Day 1 dosing. Minor procedures, such as biopsies, dental work, or placement of a port or intravenous (IV) line for infusion are permitted.
 - b. Have ongoing clinically significant anti-cancer therapy-related toxicities Common Terminology Criteria for Adverse Events (CTCAE) Grade >1 . In specific cases, patients whose toxicity has stabilized or with Grade 2 non-hematologic toxicities can be allowed following documented approval by the Sponsor's Medical Monitor
 - c. Had last dose of previous anti-cancer therapy ≤ 14 days prior to Day 1 dosing

- d. Palliative radiotherapy >14 days prior to the study is allowed
- e. Received investigational drugs in other clinical trials within 28 days, or 5 half-lives of the investigational drug (whichever is shorter), prior to C1D1
- 7. Live-attenuated vaccine (e.g., nasal spray influenza vaccine) ≤14 days prior to the intended C1D1
- 8. Impairment of gastrointestinal (GI) function or GI disease that could significantly alter the absorption of selinexor (e.g. vomiting, or diarrhea that is CTCAE v5.0 grade >1).
- 9. Life expectancy <4 months based on the opinion of the Investigator
- 10. Active pneumonitis requiring steroid therapy.
- 11. Uncontrolled (i.e., clinically unstable) infection requiring parenteral antibiotics, antivirals, or antifungals within 7 days prior to first dose of study treatment; however, prophylactic use of these agents is acceptable (including parenteral).
- 12. Any life-threatening illness, medical condition, or organ system dysfunction which, in the Investigator's opinion, could compromise the patient's safety, prevent the patient from giving informed consent, or being compliant with the study procedures.
- 13. Female patients who are pregnant or lactating.
- 14. Active hepatitis B virus treated with antiviral therapy for hepatitis B within 8 weeks with a viral load >100 IU/mL.
- 15. Untreated hepatitis C virus positive without documentation of negative viral load per institutional standard.
- 16. Human immunodeficiency virus positive with CD4+ T-cells ≤ 350 cells/uL, positive viral load per institutional standard, and a history of acquired immunodeficiency syndrome - defining opportunistic infections in the last year.

Study Treatment Cohorts and Dosing

All patients will receive:

- selinexor 80 mg PO QW and
- pembrolizumab therapy, 400 mg IV Q6W on Day 1, per the Keytruda® USPI.

In order to minimize nausea, unless contraindicated all patients must receive 2 anti-emetics initially: a 5-hydroxytryptamine 3 (5-HT3) antagonist (ondansetron 8 mg or equivalent), starting 30-60 minutes before administration of selinexor and continued 2-3 times daily for at least 2 days after selinexor dosing. A neurokinin-1(NK-1) antagonist or another anti-emetic agent should be used as per the label per National Comprehensive Cancer Network (NCCN) Guidelines. Alternative or additional anti-emetic agents may be used if the patient does not tolerate or has inadequate anti-emetic effect with 5-HT3 antagonists.

Duration of Treatment and Follow-up:

Patients will receive study treatment until disease progression, toxicity or withdrawal from the study, whichever occurs first. Disease response or progression will be assessed Q9W for the first 6 months, then every 3 months thereafter. Note: per Investigator's discretion, and upon discussion with the Sponsor Study Director, patients with a prolonged response or stable disease can discontinue pembrolizumab after 24 months of treatment and continue with selinexor monotherapy.

Patients will be followed for survival after the end of treatment (EoT) visit every 3 months for 12 months, or until withdrawal of consent, death, or the end of study (i.e., when the last patient in the study has been followed up on study treatment for at least 1 year, or completed at least 6 months of survival follow-up period after their last dose of study treatment, has withdrawn consent, has died, or has been lost to follow-up), whichever occurs first. End of treatment imaging will be performed ≤ 28 days after treatment discontinuation for patients who discontinue for reasons other than PD if their previous scan was performed >3 weeks before EoT.

After discontinuation of study treatment, patients will also be followed for safety 30 days after EoT and then every 3 months for 12 months and for PFS approximately every 3 months after EoT visit until PD, death or initiation of the subsequent anti-melanoma treatment (if a patient discontinues from the treatment due to reasons other than PD).

Statistical Methods:

CCI

Analysis Populations:

The modified intent-to-treat (mITT) population will consist of all patients who receive at least one dose of any study treatment.

The safety population will include all enrolled patients who receive at least 1 dose of both study drugs.

Efficacy Analyses:

The primary efficacy endpoint of ORR (proportion of patients who achieve CR or PR) will be analyzed for each arm separately on the modified intent-to-treat (mITT) population which consists of all enrolled patients who received any study treatment. Estimated ORR with 95% confidence interval (CI) will be summarized for each arm.

Analyses of other efficacy endpoints will be specified in Section 12 of the protocol and the Statistical Analysis Plan (SAP)

Safety Analysis:

Continual monitoring of safety data will be performed by the independent Data Safety Monitoring Board (DSMB). Adverse events and concomitant medications will be coded according to medical dictionary for regulatory activities (MedDRA) and WHO Drug, respectively. Safety analyses will be performed on the Safety Population and will be presented by actual treatment arm.

3.2. Schedule of Assessments

Table 1: Schedule of Assessments for Study XPORT-MEL-033 (42-Day Cycle)

Activity/Assessment	Screening ^a D -28 to -1	Cycles* 1			Cycles* ≥ 2			EoT Visit ≤ 28 Days Post-Treatment Discontinuation	Follow-up Visit ^b	
		D1	D3±2D	D15/D29 ±3D	D1	D3±2D	D15/D29 ±3D		30 days after EoTVisit +7D	Every 3 months until 12 months ±14D
Procedures										
Informed Consent	X									
Inclusion/Exclusion	X									
Demographics	X									
Medical history	X									
Concomitant Medications Review	X	Continuous					X	X	X	
Prior Melanoma Therapy	X									
Eligibility confirmation by Sponsor ^c	X									
ECOG Daily Living Performance Score	X	X		X						
Nutritional Counselling	X	Throughout, as needed								
Vital signs including weight	X	X		X			X			
Physical Exam – full	X						X		X	
Physical Exam – symptom directed		X		X				X		
Adverse Events ^d		Continuous								
Telephone contact ^e			X					X	X	
Collection of information regarding antineoplastic therapy after EoT								X	X	
Laboratory										
Hematology and Serum Chemistry	X	X		X	X		X	X		

Activity/Assessment	Screening ^a	Cycles* 1			Cycles* ≥2			EoT Visit	Follow-up Visit ^b	
		D -28 to -1	D1	D3±2D	D15/D29 ±3D	D1	D3±2D	D15/D29 ±3D	≤28 Days Post-Treatment Discontinuation	30 days after EoTVisit +7D
LDH	X	X			X			X		
Pregnancy test ^f	X	X						X	X	
CCI										
Drug Administration										
Selinexor		Selinexor will be administered once weekly (Days 1, 8, 15, 22, 29, 36 of 42-day cycle)								
Pembrolizumab		Pembrolizumab will be administered on Day 1 once every 6 weeks								
Anti-tumor Activity										
Tumor assessment by CT or MRI Scan	X	Tumor assessment will be performed every 9 weeks for 6 months, then every 3 months thereafter						X		

CT = computed tomography; D = day; ECOG = Eastern Cooperative Oncology Group; EoT = end of treatment; FU = follow-up; hCG = human chorionic gonadotropin; LDH = lactate dehydrogenase; MRI = magnetic resonance imaging; PDn = pharmacodynamics

* Cycles are 6 weeks in length.

^a Procedures that are performed as part of standard of care should not be repeated if they are within the screening window and are done prior to signing the ICF.

^b After discontinuation of study treatment for reasons other than PD, disease assessments should continue to be performed every 3 months until progression, start of new therapy or withdrawal of consent.

^c Eligibility form with past melanoma care, length of treatment, and best response will be reviewed and approved by Sponsor prior to randomization.

^d AEs are recorded after first dose of study treatment and at any time the patient communicates an AE upon inquiry during each visit or phone call, or an AE is assessed by the Investigator, up until 30 days after EoT.

^e Telephone contact will be made on C1D3 to evaluate supportive care medications, concomitant medications, and adverse events, and to adjust supportive care as appropriate. After discontinuation of study treatment, follow-up phone calls will be performed 30 days after EoT visit and every 3 months until 12 months documenting start of new therapy and survival status.

^f Female patients of childbearing potential must have a negative serum hCG pregnancy test within 3 days prior to first study dose on C1D1. A urine hCG test is allowed if serum hCG test is not available.

CCI

CCI

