10. STUDY ASSESSMENTS AND PROCEDURES

Study procedures and their timing are summarized in the Schedule of Assessments (SoA).

- Immediate safety concerns should be discussed with the Sponsor's Medical Monitor immediately upon occurrence or awareness to determine if the patient should continue or discontinue study treatment.
- Adherence to the study design requirements, including those specified in the SoA, is essential and required for study conduct.
- All screening evaluations must be completed and reviewed to confirm that potential patients meet all eligibility criteria. The Investigator will maintain a screening log to record details of all patients screened and to confirm eligibility or record reasons for screening failure, as applicable.
- Procedures conducted as part of the patient's routine clinical management (e.g., blood count) that were obtained prior to signing of the informed consent form (ICF) may be utilized for screening purposes provided the procedures met the protocol-specified criteria and were performed within the time frame defined in the SoA.
- All protocol defined assessments on clinic visit days (when study drug is given) should be completed prior to study drug dosing.

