10.5.3. ECOG Performance Status

The ECOG performance status ([Oken, 1982](#)) will be assessed at Screening to determine eligibility of the patient and also during the study as indicated in the SoA ([Appendix 4](#)).

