2.5. Baseline Measurement

In general, the baseline value is defined as latest value prior to the first dose of study treatment. In the case an assessment is performed on the same date as the first dose, but it is impossible to determine the evaluation time relative to the time of taking the first dose, the evaluation time will be assumed to be following the protocol-defined schedule.

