5.4. Vital Signs, ECOG, and Physical Examination Variables

Assessment of vital signs are performed during screening, day 1 of each cycle, and the end of treatment visit. The examinations include height (measured during screening visit only), weight, temperature, heart rate, and systolic and diastolic blood pressure.

An ECOG score assessment with grades 0-5 will be performed during screening and day 1 of each cycle.

The actual value and change from baseline to each on-study evaluation will be summarized for vital signs including pulse, temperature, systolic blood pressure, diastolic blood pressure, BSA and weight. Shift tables that present changes from baseline to worst on-study and last on-study for systolic blood pressure, diastolic blood pressure, and ECOG performance status values will be produced.

Abnormal vital signs results will be summarized in the threshold/range analyses.

All vital signs, ECOG, and physical examination findings will be presented in data listings.

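### ECOG is not scheduled at the end-of-treatment visit, so the planned shifts to worst and last on-study ECOG can miss decline around stopping (minor)

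*Protocol*

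**What the plan says.** The clearest statement of the schedule is in SAP 5.4. For performance status it says: "An ECOG score assessment with grades 0-5 will be performed during screening and day 1 of each cycle". For vital signs, in the same section, it says: "Assessment of vital signs are performed during screening, day 1 of each cycle, and the end of treatment visit". The EoT visit is named for one and not for the other.

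The protocol adds no further ECOG visit. Section 10.5.3 says that performance status "will be assessed at Screening to determine eligibility of the patient and also during the study as indicated in the SoA", which refers the reader back to Table 1. There the row "ECOG Daily Living Performance Score" has three marks, none of them under EoT or follow-up. A table footnote gives the cycle length: "Cycles are 6 weeks in length".

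The planned analysis, also in SAP 5.4, is: "Shift tables that present changes from baseline to worst on-study and last on-study for systolic blood pressure, diastolic blood pressure, and ECOG performance status".

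Two rules fix what counts as baseline. SAP 2.5 states that in general "the baseline value is defined as latest value prior to the first dose of study treatment". Protocol Section 10 states: "All protocol defined assessments on clinic visit days (when study drug is given) should be completed prior to study drug dosing".

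**The concern.** A shift to the worst or last on-study value is informative only if values are collected close to the time when patients get worse. Here they are collected when a patient begins a new cycle and not when treatment ends. Patients leave treatment because the disease progresses, because of toxicity or because they withdraw. Those with no post-baseline value, or with an old one, may therefore include more patients whose function had declined. Protocol 4.5 names fatigue, anorexia and weight loss among the common selinexor-related events, so performance status is a natural companion measure. At stake is whether the ECOG shift table gives a fair picture of function on treatment. Blood pressure gets the same shift tables, but its schedule runs through EoT.

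**Working it through.** The plan states no figure that depends on this schedule, so there is nothing to reproduce. The check is a comparison of the schedule texts followed by day arithmetic.

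**1. Which visits carry ECOG.** The columns of Table 1 are displaced in the extracted text, so the row needs care.
- Read literally, the third ECOG mark falls under Cycle 1 Day 15/29.
- The same literal reading puts the follow-up telephone calls at EoT and 30 days, against footnote e (30 days after EoT, then every 3 months). It also puts vital signs at Day 15/29 of later cycles, against SAP 5.4.
- Moving the later marks in these rows one column to the right settles both conflicts. It gives ECOG at screening, Cycle 1 Day 1 and Day 1 of later cycles, as in the SAP. The displacement is not uniform: the hematology and LDH rows read sensibly without a shift. SAP 5.4 is therefore the firmer source.
- One comparison does not depend on the columns. The vital-signs row has the same first three marks as ECOG plus a fourth, which SAP 5.4 identifies as EoT. The ECOG row has no fourth mark.

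On either reading, ECOG is not scheduled at EoT.

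**2. First scheduled post-baseline value.** Cycle 1 Day 1 assessments precede dosing and baseline is the latest pre-dose value, so the Cycle 1 Day 1 ECOG is baseline. The next scheduled ECOG is Cycle 2 Day 1:

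42 + 1 = study Day 43 (as in SAP Table 2-1).

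A patient who stops before Day 43 has no scheduled post-baseline ECOG.

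**3. Age of the last scheduled value for later stops.**
- Stop on the last day of a cycle: 42 − 1 = 41 days after the Day 1 ECOG.
- Stop decided at the Week 9 scan: 9 × 7 + 1 = Day 64. Cycle 2 Day 1 is Day 43, so the gap is 64 − 43 = 21 days.
- Stop decided at the Week 18 scan: 18 × 7 + 1 = Day 127. Cycle 4 Day 1 is 3 × 42 + 1 = Day 127, so the gap is 0 days.
- Protocol 6.2 allows the EoT visit up to 28 days after discontinuation. The longest interval from last ECOG to EoT is 41 + 28 = 69 days, of which 28 fall after the stop.

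**4. Illustration of scale.** The documents give no Cycle 1 discontinuation rate. Assuming 5% to 20%:
- 40 × 0.05 = 2 patients; 40 × 0.20 = 8 patients.
- Chance of at least one such patient in an arm of 20: 1 − 0.95^20 = 0.64 at 5%, and 1 − 0.80^20 = 0.99 at 20%.

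**The case against.** **Missing patients need not vanish.** Protocol 12.1 calls for missing values to appear as their own category in categorical tables. SAP 2.2 takes the analysis population as the default denominator and permits a missing category. This stands: a patient without a post-baseline ECOG can remain visible, and it is too strong to say that such patients drop out of the table. But SAP 2.2 only permits the category, and showing a gap does not fill it.

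**The harms are captured elsewhere.** Adverse events are graded and collected through 30 days after the last dose or until new therapy. Weight is measured with vital signs at EoT. Reasons for stopping, and events leading to it, are tabulated. This also stands, and it limits the damage: toxicity is unlikely to be hidden by the ECOG table alone.

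**ECOG is not a named endpoint.** The safety endpoint lists adverse events, vital signs, laboratory results and physical examination. The safety analyses are descriptive. This stands and sets the priority.

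**Other values may exist.** A stop decided at a Day 1 visit has a same-day ECOG, and unscheduled assessments are possible. So the tables can miss decline; they do not always miss it. No unscheduled ECOG is required, however. SAP 5.3.2 says that laboratory shift tables include unscheduled visits, and SAP 5.4 says nothing similar for ECOG.

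**A stronger reading.** A reader might take the median progression-free survival figures in the protocol, assume exponential time on treatment, and infer that 10% to 20% stop before Day 43. With 42/30.44 = 1.38 months, 1 − exp(−ln 2 × 1.38/8.8) = 10% and 1 − exp(−ln 2 × 1.38/4.2) = 20%, or about 4 to 8 of 40. The documents do not support this as an estimate. The 8.8 months comes from a study of a different selinexor schedule that included checkpoint-inhibitor-naïve patients, and the 4.2 months from lenvatinib plus pembrolizumab. Progression-free survival is not time on treatment. The first on-treatment scan is at Week 9 (Day 64), so no scheduled scan can prompt a stop before Day 43.

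**Conclusion.** The mismatch is real but minor. On the SAP schedule, ECOG is not collected at EoT although shifts to worst and last on-study ECOG are planned. Patients who stop before Day 43 have no scheduled post-baseline value. For the rest, the last scheduled value can precede the stop by up to about 41 days. The shift tables can therefore miss decline around discontinuation and may lean towards preserved function.

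A reader might go further and conclude that the tables will overstate function. The documents do not establish that: the bias is plausible in direction, but its size is unknown and a missing category would expose part of it. The number of patients is likewise unknown, and the 2 to 8 of 40 rests on an assumed 5% to 20%. The Day 43 statement rests on SAP 5.4. If the Table 1 mark really belonged to Cycle 1 Day 15/29, some early stoppers would have a value, but the EoT omission would remain. No efficacy result and no named safety endpoint changes.

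**What to change.** Add an ECOG mark to the EoT column of Table 1, and reword SAP 5.4 so that ECOG has the same time points as vital signs: screening, Day 1 of each cycle and EoT. State in SAP 5.4 that the EoT value counts towards both the worst and the last on-study shift, and that patients with no post-baseline ECOG appear as a missing category.

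The cost is one table cell, a short SAP edit and one extra data item, about a minute at a visit that already takes place. The gain is limited in two ways: the EoT value may be taken up to 28 days after stopping, and patients who do not attend EoT stay missing. The change is still worth making before more patients stop, because an ECOG not recorded at the time cannot be recovered.
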